### **Statistical Considerations for Biomarkers:**

Preliminary data was analyzed on a retrospective series extracted from previously built tissue microarrays with human bladder cancer specimens at various stages. For this analysis we selected 108 and 99 patients with stage Ta and T1 on each biomarker, Ki-67 and TUNEL, respectively.

Stage	n	
	Ki-67	TUNEL
TIS	1	1
TA	78	73
T1	29	25
T1A	1	1
T2A	11	8
T2B	3	2
T3A	22	10
T3B	13	8
T4A	5	3
T4B	2	1
NA	1	1
Total	166	133

Mean expression with standard deviation for each subject with Ta or T1 disease with more than one core (Ki-67, n=82; TUNEL, n=65) was computed. These data are presented in the boxplots below. Median values of these means and standard deviations were used in the calculation of power and sample size. In the plot, the red mark is the mean and the horizontal line is the median.

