### Calculation of sample size and power for Ki-67 analysis

The maximum sample size of 17 will have 85.6% power to detect a difference in means of 30% (-1.101 or 1.101, e.g. a first condition mean,  $\mu_1$ , of 3.670 and a second condition mean,  $\mu_2$ , of 2.569), assuming a standard deviation of differences of 1.41, using a paired t-test with a 0.050 two-sided significance level. Alternatively, the minimum sample size of 9 will have 51.5% power. With the maximum sample size, a 27.8% detectable difference (-1.021 or 1.021) could be significantly identified under  $\alpha=0.05$  and power=0.8 assumptions.

Significant level (2-sided)	0.05	0.05	0.05
First condition mean	3.67	3.67	3.67
Second condition mean	2.569	2.569	2.613
Mean difference	1.101	1.101	1.021
Standard deviation of differences	1.41	1.41	1.41
Power (%)	85.6	51.5	80.0
N	17	9	17

**Ki-67:** table for paired t-test power and sample size results

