### Calculation of sample size and power for TUNEL analysis

The maximum sample size of 17 will have 96.7% power to detect a difference in means of 30% (-5.1 or 5.1, e.g. a first condition mean,  $\mu_1$ , of 17 and a second condition mean,  $\mu_2$ , of 22.1), assuming a standard deviation of differences of 5.13, using a paired t-test with a 0.050 two-sided significance level. Alternatively, the minimum sample size of 9 will have 74.1% power. With the maximum sample size, a 21.8% detectable difference (-3.71 or 3.71) could be significantly identified under  $\alpha=0.05$  and power=0.8 assumptions.

Significant level (2-sided)	0.05	0.05	0.05
First condition mean	17	17	17
Second condition mean	22.1	22.1	20.85
Mean difference	5.1	5.1	3.71
Standard deviation of differences	5.13	5.13	5.13
Power (%)	96.7	74.1	80
N	17	9	17

**TUNEL:** table for paired t-test power and sample size results

In summary, the Simon's optimal design, and the maximum sample size of 17 subjects, will yield an 85.6% and 96.7% power (two-sided, paired t-test with 5% alpha) to identify 30% change in the Ki-67 and the TUNEL assays, respectively. Similarly, the minimum sample size of 9 will yield 51.5% and 74.1% power, respectively. Modulation of pre vs. post-treatment biomarker endpoints will be summarized and compared using the paired t-test or nonparametric paired tests for quantitatively measured biomarkers, including Ki-67, and TUNEL. Independent analyses will likewise be employed to compare these biomarkers measured between normal mucosa and marker bladder tumor, such as the STUDENT T-Test or the non-parametric counterpart (Mann-Whitney test), as appropriate. We will assess Pearson's correlation. We will also assess the correlations of pretreatment expression levels of ER $\alpha$  and ER $\beta$  (wild type and its isoforms) with rates of positive response. Descriptive statistics will be calculated to summarize these biomarkers at pretreatment, post-treatment, difference from pre to post-treatment, and percent change from pre to post-treatment. Histologic effect will also be considered as a secondary endpoint in determining response to therapy. Histologic effect in the lesion will be summarized descriptively using frequencies and proportions before and after treatment.

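### Ki-67 power at N=9 and two table means do not follow from their stated inputs, and the N=17 biomarker powers count all 17 response-evaluable patients as tumour pairs

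*Combined protocol and SAP*

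**What the plan says.** Under Statistical Considerations for Biomarkers, the combined protocol and SAP takes its planning inputs from a retrospective series of tissue microarrays. It computed "Mean expression with standard deviation for each subject with Ta or T1 disease with more than one core" and adds that "Median values of these means and standard deviations were used in the calculation of power and sample size".

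The Ki-67 calculation uses a first mean of 3.67 and a 30% change of 1.101, "assuming a standard deviation of differences of 1.41, using a paired t-test with a 0.050 two-sided significance level". It states 85.6% power at N=17 and then: "Alternatively, the minimum sample size of 9 will have 51.5% power". It continues: "With the maximum sample size, a 27.8% detectable difference (-1.021 or 1.021"), at 80% power. The third column of the Ki-67 table lists that difference beside a second mean of 2.613.

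The TUNEL calculation uses a first mean of 17 and a change of 5.1, "assuming a standard deviation of differences of 5.13, using a paired t-test with a 0.050 two-sided significance level". It states 96.7% at N=17, 74.1% at N=9, and a detectable difference of 3.71. Its third column gives a second mean of 20.85.

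The summary says that the maximum of 17 subjects "will yield an 85.6% and 96.7% power (two-sided, paired t-test with 5% alpha") for a 30% change in Ki-67 and TUNEL respectively, and that "the minimum sample size of 9 will yield 51.5% and 74.1% power, respectively".

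Three other sections bear on this:

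- **Sample Size:** the 17 are eligible patients with at least 30 days of tamoxifen. Paired tumour tissue is not required.
- **Overall study description:** post-treatment tissue is taken after the 12-week course. A complete responder has only the tumour bed biopsied, and the definitive marker-lesion resection is described as a source of immunohistochemistry material when there has been no response.
- **End-points/Statistical considerations:** a biopsy free of cancer counts as success, including the case of no viable tumour.

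**The concern.** Three things do not sit together.

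1. One stated power and two tabulated means appear not to follow from the inputs printed beside them.
2. The power statement is unconditional on tissue. A paired test on the marker lesion needs scorable tumour before and after treatment, and a patient can be evaluable for response without it. The move from 19 enrolled to 17 evaluable makes no allowance for this.
3. Spread among cores from one specimen set is not the same quantity as the spread of pre/post changes between patients, and no link between the two is given.

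These tests address Aim 1c, the tissue evidence for the apoptosis and proliferation mechanism in Hypothesis 1. A reader would take the stated powers as settled. The Aim 1c analysis text does not say what the paired test does with a patient who has no tumour to score, so that choice would otherwise be made after the data are seen.

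**Working it through.** **Inputs (Ki-67 and TUNEL calculation sections).** Paired t-test, two-sided 5%. Ki-67: difference 1.101, SD of differences 1.41. TUNEL: difference 5.1, SD of differences 5.13.

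**Formula.** With n pairs, df = n − 1 and noncentrality λ = (difference / SD) × √n. Power is the probability that a noncentral t variable with these parameters lies beyond ±t(0.975, df).

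**Step 1: the plan's own figures.**

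| Marker | n | λ | critical t | Recomputed | Stated |
|---|---|---|---|---|---|
| Ki-67 | 17 | 3.220 | 2.120 | 85.6% | 85.6% |
| TUNEL | 17 | 4.099 | 2.120 | 97.0% | 96.7% |
| TUNEL | 9 | 2.982 | 2.306 | 74.3% | 74.1% |
| Ki-67 | 9 | 2.343 | 2.306 | **53.9%** | **51.5%** |

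Three cells agree to within 0.3 points; Ki-67 at N=9 is 2.4 points off. A simulation of 400,000 trials gave 54.1%. Rounding of the SD (1.405 to 1.415) gives only 53.6% to 54.2%. A one-sided t-test (68.9%) or a normal approximation (64.9% two-sided, 75.7% one-sided) does not explain the figure. Shrinking n by 3/π, as for a rank test, does give 51.5%. But the text specifies a t-test, and the same adjustment gives 83.7%, 96.3% and 71.7% where the plan prints 85.6%, 96.7% and 74.1%.

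**Step 2: third-column means.**

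- Ki-67: 3.67 − 2.613 = 1.057, not 1.021. The listed difference requires 3.67 − 1.021 = 2.649.
- TUNEL: 20.85 − 17 = 3.85, not 3.71. The listed difference requires 17 + 3.71 = 20.71.

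The listed differences reproduce the stated 80% power at n = 17 (80.0% and 79.9%). The printed means would imply 82.7% for each. The means are therefore the slips, and the detectable differences in the prose are right.

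**Step 3: fewer tumour pairs.** Difference held at 30%, SDs as stated:

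| Pairs | Ki-67 | TUNEL |
|---|---|---|
| 17 | 85.6% | 97.0% |
| 15 | 80.3% | 94.7% |
| 14 | 77.1% | 93.0% |
| 12 | 69.3% | 87.9% |

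The documents do not give the number of pairs that would be lost, so each row is an assumption. For scale, the design alternative P1 = 0.30 gives 17 × 0.30 = 5.1 expected responders. If every one lacked scorable tumour, 17 − 5.1 = 11.9 pairs would remain, roughly the 12-pair row. Twelve is not a floor: six or more responders has probability 0.40 at that rate. At P0 = 0.05 the expected number of responders is 17 × 0.05 = 0.85, so loss through response would be small.

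**Step 4: the SD.** The biomarker section describes a median of per-subject SDs across cores; the calculations use 1.41 and 5.13 as SDs of differences. As an illustration only, suppose they are single-time SDs and the pre/post correlation is ρ. The SD of differences is then SD × √(2(1 − ρ)), and power at n = 17 (Ki-67/TUNEL) is:

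- ρ = 0: 57.1%/77.7%
- ρ = 0.25: 69.5%/88.1%
- ρ = 0.5: 85.6%/97.0%
- ρ = 0.75: 98.9%/more than 99.9%

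The stated powers could thus be too high or too low. As a measure of margin, with 17 pairs power falls to 80% at an SD of 1.52 for Ki-67 (1.52/1.41, 8% larger) and 7.05 for TUNEL (7.05/5.13, 37% larger).

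**The case against.** The best case for leaving the text alone has four parts.

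**The slips are small.** This stands. The 51.5% understates power, the 0.3-point TUNEL difference is minor, and the detectable differences in the prose are correct.

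**The source of the SDs is stated, and the boxplots are not visible in the text reviewed.** This stands too. A reader might infer that the SDs are too small, because spread among cores contains no between-patient variation in drug effect. The documents do not support that as a net conclusion. They do not show whether 1.41 and 5.13 are raw or converted. Aim 2 Procedures also says the final resection gives much larger fragments than the small pretreatment biopsy, which could offset the omission.

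**Twelve pairs is pessimistic.** Agreed. Partial responders, and complete responders with a positive bed biopsy, still have tumour according to the response table. Aim 2 Procedures describes the final resection without limiting it to non-responders. The no-response wording in the Overall study description should not be read as removing every responder.

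**Power need not fall as the drug works better.** A reader might infer that greater activity means lower Ki-67 power. That holds only if the mean change stays at 30%. The background section links proliferation and apoptosis effects to response, so a more active drug may bring a larger change. At the stated SD, a 33.6% change with 14 pairs, or 36.8% with 12, restores 85.6%. Losing the best responders could work the other way. The net direction is unknown.

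None of this answers the narrower point: the power statement assumes 17 tumour pairs, and the plan does not secure them.

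**Conclusion.** The point holds in three parts of unequal weight.

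1. **Certain, no assumption needed.** Ki-67 power at N=9 is 53.9%, and the two third-column means should be 2.649 and 20.71. TUNEL at N=17 computes to 97.0% against 96.7%, a minor difference.
2. **Holds, with its size conditional.** The N=17 powers are correct for 17 tumour pairs but are stated for 17 response-evaluable patients. At a fixed 30% change and the stated SDs, losing two pairs brings Ki-67 to 80.3% and losing three to 77.1%, just below the 80% that the plan uses for its detectable differences. TUNEL stays at 87.9% even with 12 pairs. It would be wrong to infer that pairs are lost only among responders: a patient becomes evaluable after 30 days of tamoxifen, and one without week-12 tissue also contributes no pair, whatever the response.
3. **Clarification only.** The step from across-core SDs to SDs of pre/post differences is not explained. No error of known direction or size can be claimed.

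The Simon design and its sample size do not depend on any of this. Loss of pairs through absence of tumour in the marker lesion does not affect the normal-mucosa pairs. A stop after stage one requires no responses in nine, so no pair would be lost there through response.

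**What to change.** **Numbers (Ki-67 and TUNEL calculation sections).** Change Ki-67 power at N=9 from 51.5% to 53.9% in the text, table and summary. Change 2.613 to 2.649 and 20.85 to 20.71. Use 97.0% for TUNEL at N=17 in all three places, so that it agrees with the conditional statement below. If the table is regenerated, TUNEL at N=9 would read 74.3% instead of 74.1%, which is of no consequence.

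**Power statement (summary after the TUNEL table).** Replace the unconditional claim with, for example: *With 17, 15 or 14 marker-lesion pairs, and assuming SDs of differences of 1.41 and 5.13, power for a 30% change is 85.6%, 80.3% or 77.1% for Ki-67 and 97.0%, 94.7% or 93.0% for TUNEL. A pessimistic case of 12 pairs, which is not a lower limit, gives 69.3% and 87.9%.*

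**SD (Statistical Considerations for Biomarkers).** Add one sentence saying how 1.41 and 5.13 were obtained from the core-level data and why they are used as SDs of differences.

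**Analysis (Specific Aim 1c).** Report the marker-lesion paired test with its number of pairs and label it as conditional on residual tumour. List beside it the number and response category of patients without a scorable pair.

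**Cost.** A few figures and sentences, with no added patients, tissue or procedures. The downside is that the stated Ki-67 power becomes less favourable.

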### Calculation of sample size and power for Ki-67 analysis

The maximum sample size of 17 will have 85.6% power to detect a difference in means of 30% (-1.101 or 1.101, e.g. a first condition mean,  $\mu_1$ , of 3.670 and a second condition mean,  $\mu_2$ , of 2.569), assuming a standard deviation of differences of 1.41, using a paired t-test with a 0.050 two-sided significance level. Alternatively, the minimum sample size of 9 will have 51.5% power. With the maximum sample size, a 27.8% detectable difference (-1.021 or 1.021) could be significantly identified under  $\alpha=0.05$  and power=0.8 assumptions.

Significant level (2-sided)	0.05	0.05	0.05
First condition mean	3.67	3.67	3.67
Second condition mean	2.569	2.569	2.613
Mean difference	1.101	1.101	1.021
Standard deviation of differences	1.41	1.41	1.41
Power (%)	85.6	51.5	80.0
N	17	9	17

**Ki-67:** table for paired t-test power and sample size results

### Calculation of sample size and power for TUNEL analysis

The maximum sample size of 17 will have 96.7% power to detect a difference in means of 30% (-5.1 or 5.1, e.g. a first condition mean,  $\mu_1$ , of 17 and a second condition mean,  $\mu_2$ , of 22.1), assuming a standard deviation of differences of 5.13, using a paired t-test with a 0.050 two-sided significance level. Alternatively, the minimum sample size of 9 will have 74.1% power. With the maximum sample size, a 21.8% detectable difference (-3.71 or 3.71) could be significantly identified under  $\alpha=0.05$  and power=0.8 assumptions.

Significant level (2-sided)	0.05	0.05	0.05
First condition mean	17	17	17
Second condition mean	22.1	22.1	20.85
Mean difference	5.1	5.1	3.71
Standard deviation of differences	5.13	5.13	5.13
Power (%)	96.7	74.1	80
N	17	9	17

**TUNEL:** table for paired t-test power and sample size results

In summary, the Simon's optimal design, and the maximum sample size of 17 subjects, will yield an 85.6% and 96.7% power (two-sided, paired t-test with 5% alpha) to identify 30% change in the Ki-67 and the TUNEL assays, respectively. Similarly, the minimum sample size of 9 will yield 51.5% and 74.1% power, respectively. Modulation of pre vs. post-treatment biomarker endpoints will be summarized and compared using the paired t-test or nonparametric paired tests for quantitatively measured biomarkers, including Ki-67, and TUNEL. Independent analyses will likewise be employed to compare these biomarkers measured between normal mucosa and marker bladder tumor, such as the STUDENT T-Test or the non-parametric counterpart (Mann-Whitney test), as appropriate. We will assess Pearson's correlation. We will also assess the correlations of pretreatment expression levels of ER $\alpha$  and ER $\beta$  (wild type and its isoforms) with rates of positive response. Descriptive statistics will be calculated to summarize these biomarkers at pretreatment, post-treatment, difference from pre to post-treatment, and percent change from pre to post-treatment. Histologic effect will also be considered as a secondary endpoint in determining response to therapy. Histologic effect in the lesion will be summarized descriptively using frequencies and proportions before and after treatment.

### **Statistical considerations on the proposed analyses of the secondary aims, including the biomarker experiments**

**Specific Aim 1b:** We will assess the histologic aspect of both normal tissue and the bladder cancer marker lesion biopsies before and after treatment and compare for the presence of fibrosis, scarring, tumor necrosis and apoptosis. These data will be measured and quantified using light microscopy so percent positivity can be evaluated. Comparisons will be made between normal and tumor tissues (independent samples analysis), and also between pre and post-treatment on both normal and tumor tissues (paired samples analysis) to evaluate the effect with tamoxifen treatment. Non-parametric tests will be utilized as appropriate.

**Specific Aim 1c:** We will compare pre and post-treatment levels of immunohistochemistry staining levels of both the normal tissue and the marker lesion to detect changes in expression of TUNEL and Ki-67, associated with treatment (paired samples analysis). Nuclear immunoreactivity will be assessed by light microscopy and percent positive stained nuclei calculated. The percentiles will be analyzed as a continuous variable. Just like above, non-parametric tests will be utilized as appropriate.

The modulation of pre vs. post-treatment biomarker endpoints will be summarized and compared using the paired t-test or nonparametric paired tests as appropriate for quantitatively measured biomarkers, including Ki-67, and TUNEL. Independent analyses will likewise be employed to compare these biomarkers measured between normal mucosa and marker bladder tumor. We will

also assess the correlations of TUNEL and Ki-67 with rates of positive response. Descriptive statistics will be calculated to summarize these biomarkers at pretreatment, post-treatment, difference from pre to post-treatment, and percent change from pre to post-treatment. Histologic effect will also be considered as a secondary endpoint in determining response to therapy. Histologic effect in the lesion will be summarized descriptively using frequencies and proportions before and after treatment.

**Specific Aim 1d:** Toxicity data will be presented and summarized using descriptive statistics, tabulated using frequencies and percentages.

**Specific Aim 2a and 2b:** All data will be presented and summarized using descriptive statistics. The percentage of positive cells with nuclear immunoreactivity is recorded on a semi-quantitative scale: results are categorized as negative (< 10% cell labeling) or positive ( $\geq$  10% cell labeling). Normal breast tissue and transfected cells with known ER will be used as positive control and normal tissues such as liver and spleen, as well as cells transfected with empty vectors will be used as negative controls.

We will correlate pretreatment ER levels with the proportion of the positive response (composite endpoint of clinical PR and CR, and a final biopsy) of the marker lesion to determine associations with treatment effect. Specifically, Pearson's or Spearman's correlation coefficients will be calculated to estimate and test for significant correlations between the expression level of the ERs and the primary endpoint. Comparison of ERs expression levels from normal and bladder tumor tissues measured prior to treatment will also be performed using independent sample tests as described above. Non-parametric tests will be utilized as appropriate.

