### **Collection of specimens**

A random biopsy of normal appearing mucosa remote from any tumor will be required pre and post-treatment. All immunohistochemistry studies will be performed on formalin-fixed paraffin-embedded tissue. Tissue destined to mRNA analysis will be directed to the research laboratory for analysis. . At the end of the trial, these specimens will be destroyed in an appropriate manner, according to the BCM rules and regulations.

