### Office visit on 2nd Resection only occurs if patient had a single Tumor during 1st Resection. All patients with Multiple tumors at 1st Resection will have 2nd Resection in an outpatient hospital setting.

#### Completed per PI description

## **Procedures:**

**Aim 1 Procedures:** Transurethral resection of bladder tumors is a well-defined surgical technique used for diagnosis, staging, and treatment of bladder tumors of different stages. Briefly, patients undergo general anesthesia. Under proper aseptic technique, an optical resectoscope with video imaging capabilities is introduced into the bladder retrogradely via the urethra. The bladder tumor is resected using a resection loop connected to an electric source. The technique involves scooping movements of the loop, while cauterization is applied, to allow concomitant tissue cut and hemostasis. Measurement of the lesions will be performed by comparison with the standardized size of the resection loop.

Collection of samples: Biopsies of the marker lesion and normal appearing mucosa located remotely from the marker lesion will be processed using standard procedures for formalin fixation and paraffin embedding. These tissues will be tested by immunohistochemistry for Ki-67 and TUNEL. Each specimen will also be stained with hematoxylin and eosin to verify urothelial carcinoma histology.

**Aim 2 Procedures:** Collection of samples: Biopsies of the marker lesion and normal mucosa remote from the marker lesion will be processed using standard procedures for formalin fixation and paraffin embedding. The pretreatment biopsy of the marker lesion will be performed with a 2mm cold-cup biopsy forceps, to avoid affecting the histologic characteristics of the marker lesion. Because of the limited amount of tissue yield in this biopsy, we will only perform immunohistochemistry analyzing Ki-67, TUNEL, ER $\alpha$  and ER $\beta$ -1. The normal bladder biopsies, the resection of additional tumors synchronous to the marker lesion (in case of multiple lesions), and the final definitive resection of the marker lesion will be performed with a regular rigid biopsy forceps or resection loop, yielding much larger specimen fragments. These tissues will be tested by immunohistochemistry and RT-qPCR for the mRNA of ER $\alpha$ , ER $\beta$ -1, ER $\beta$ -2 and ER $\beta$ -5. Each specimen will also be stained with hematoxylin and eosin to verify urothelial carcinoma histology.

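### Normal mucosa and tumour come from the same patients, but the secondary normal-versus-tumour comparisons are planned with independent-samples tests

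*Combined protocol and SAP*

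**What the plan says.** Both tissues come from one cohort. The Sample Size section describes a single-arm trial. Under Overall study description, each patient's marker lesion is biopsied before treatment and normal-looking mucosa is biopsied as well. Collection of specimens adds: "A random biopsy of normal appearing mucosa remote from any tumor will be required pre and post-treatment". Procedures, Aim 1, takes the two tissues together: "Biopsies of the marker lesion and normal appearing mucosa located remotely from the marker lesion will be processed using standard procedures".

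The normal-versus-tumour tests are nevertheless unpaired in four places:

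- Aim 1b (histology): "Comparisons will be made between normal and tumor tissues (independent samples analysis"). The same sentence labels the pre/post comparison as paired.
- Aim 1c (Ki-67 and TUNEL): "Independent analyses will likewise be employed to compare these biomarkers measured between normal mucosa and marker bladder tumor".
- The summary after the TUNEL power table names the parametric test: "Independent analyses will likewise be employed to compare these biomarkers measured between normal mucosa and marker bladder tumor, such as the STUDENT T-Test". Its fallback when normality fails is worded thus: "or the non-parametric counterpart (Mann-Whitney test), as appropriate".
- Aims 2a and 2b (oestrogen receptors): "Comparison of ERs expression levels from normal and bladder tumor tissues measured prior to treatment will also be performed using independent sample tests".

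Receptor immunohistochemistry is also dichotomised at 10% labelling: "results are categorized as negative (< 10% cell labeling"), otherwise positive.

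**The concern.** Two biopsies from one bladder share the patient, the fixation and staining, and possibly the biology. An independent-samples test assumes they share nothing. If that is false, the test uses the wrong standard error. With positive correlation a real tissue difference is more easily missed; with negative correlation a false one is declared too often. The provision for non-parametric tests does not help, because the counterpart the plan names is Mann-Whitney, which is also unpaired. With 9 to 17 patients there is little information to waste, and Aim 2 sets out to evaluate receptor expression in both normal and tumour tissue.

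**Working it through.** **1. The plan's own figures.** The only biomarker power calculations are for paired pre/post t-tests at two-sided 5%. The non-centrality is (difference / SD of differences) × √n.

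- Ki-67: (1.101 / 1.41) × √17 = 3.22 on 16 df, power 85.6% (stated 85.6%).
- TUNEL: (5.1 / 5.13) × √17 = 4.10 on 16 df, power 97.0% (stated 96.7%).

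These reproduce, but they say nothing about normal versus tumour. For that comparison the documents give no SD, correlation or target difference.

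**2. The missing term.** With n pairs, tissue SDs s1 and s2 and within-patient correlation ρ:

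- true variance of the mean difference = (s1² + s2² − 2ρ·s1·s2) / n
- variance used by the independent test = (s1² + s2²) / n

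For equal SDs the ratio of standard errors, independent to paired, is 1/√(1 − ρ).

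**3. Size with equal SDs.** Assumptions: n = 17, bivariate normal data, true difference 0.7 SD for power. The planned t-test is simulated (at least 100,000 trials per setting); paired power is exact from the non-central t.

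| ρ | SE ratio | Type I error, planned | Power, planned vs paired |
|---|---|---|---|
| -0.3 | 0.88 | about 8% | 51 vs 39% |
| 0 | 1.00 | 5% | 51 vs 48% |
| 0.3 | 1.20 | about 2% | 51 vs 63% |
| 0.5 | 1.41 | 0.8% | 51 vs 77% |

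The planned test's advantage at ρ = -0.3 comes with its inflated type I error. At ρ = 0.5, larger differences shrink the gap: 88 vs 97% at 1.0 SD and 97 vs 99.6% at 1.2 SD. If the trial stops at n = 9 (ρ = 0.5, 0.7 SD) it is 23 vs 46%. Mann-Whitney behaves alike at n = 17: type I error 8% at ρ = -0.3 and 0.9% at 0.5, with power 48 vs 74% for the signed-rank test at ρ = 0.5 and 0.7 SD.

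**4. Size with unequal SDs.** Hold ρ = 0.5, n = 17 and a difference of 0.7 root-mean-square SD, scaled so that s1² + s2² = 2. The variance of a within-patient difference is then 2 − s1·s2, and the paired non-centrality is 0.7 × √(17 / variance).

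| SD ratio | Variance of difference | Non-centrality | Type I error, planned | Power, planned vs paired | Loss (from unrounded values) |
|---|---|---|---|---|---|
| 1:1 | 1.00 | 2.89 | 0.8% | 51 vs 77% | 26 points |
| 2:1 | 1.20 | 2.63 | 1.5% | 51 vs 70% | 18 points |
| 3:1 | 1.40 | 2.44 | 2.5% | 51 vs 63% | 12 points |
| 5:1 | 1.62 | 2.27 | about 3.5% | 51 vs 57% | 5 points |

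Equal SDs are therefore the upper-end case for a given positive correlation.

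**5. Where pairs exist.**

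- Before treatment, full pairs are expected for histology, Ki-67, TUNEL, and ER-alpha and ER-beta-1 immunohistochemistry. These are what the small marker biopsy can support (Overall study description; Procedures, Aim 2).
- After treatment, a complete response leaves only a biopsy of the tumour bed (Specific Aims, Aim 1a; Overall study description). Tumour values can then be missing because of response.
- Pretreatment tumour RT-qPCR, and ER-beta-2 and ER-beta-5, can come only from additional lesions in patients with several tumours. Pairs are sparse there, and one patient may contribute more than one tumour.

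**The case against.** The best defence is that little hangs on these comparisons. They are absent from the Hypotheses section, no power is claimed for them, and Aim 2a is framed mainly around pre versus post. If the correlation is positive, which is plausible for two samples from one bladder, the planned test is conservative: it loses power but creates no false claim. At zero correlation it is valid and slightly more powerful than the paired test. A large tissue difference would be found either way. All of this stands. It limits the point to a secondary analysis but does not make the test match the design.

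Three further limits also stand. The 26-point loss depends on equal SDs. Full pairs cannot be assumed after treatment. And a mixed model for incomplete pairs is not safe by default: with 17 normal and 8 tumour samples (an assumed split), a patient random-effect model holds about 5% type I error on 7 df but gives about 8% on 23 df, at correlations of 0, 0.3 and 0.5. It also cannot represent a negative correlation, and the check did not cover several tumours per patient.

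A reader might infer that the trial's efficacy conclusion or its stated biomarker power is compromised. The documents do not support that: the response endpoint, the Simon rule and the pre/post tests do not use the normal-versus-tumour comparison, and the pre/post tests are already paired. Nor do they support the reading that the plan generally inflates false positives; that needs a negative correlation.

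**Conclusion.** The mismatch is real. The plan applies independent-samples tests to matched tissue in four places, and nothing elsewhere overrides them or draws normal bladder mucosa from other people; the breast, liver and spleen tissues are assay controls. The standard errors and p-values are wrong whenever the within-patient correlation is not zero, and the sign of the correlation sets the direction.

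The size cannot be fixed from the documents. Over the assumed range of correlation (-0.3 to 0.5, equal SDs) the true level of a 5% t-test runs from about 8% down to 0.8%. The power loss at correlation 0.5 and 0.7 SD runs from 5 to 26 points across SD ratios of 5:1 to 1:1. The point is confined to secondary comparisons and should be corrected before analysis because correction is cheap.

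**What to change.** Replace the independent-samples wording in the summary after the TUNEL power table and under Aims 1b, 1c, 2a and 2b:

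1. **Pretreatment Ki-67, TUNEL, histology percent positivity, and ER-alpha and ER-beta-1 kept continuous:** paired t-test or Wilcoxon signed-rank test on tumour minus normal within patient.
2. **ER-alpha and ER-beta-1 status dichotomised at 10%:** exact McNemar test.
3. **Post-treatment comparisons:** the same paired tests among patients with residual tumour. Report the number of pairs and say that the result describes those patients only.
4. **Sparse markers (pretreatment tumour RT-qPCR, ER-beta-2, ER-beta-5):** describe them, with the number of pairs. If a mixed model with a patient random effect is used for continuous measures, fix its degrees of freedom in advance at the number of complete pairs minus one (8 − 1 = 7 in the example above).

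The cost is SAP wording and slightly more analysis, with no new patients, tissue or assays. If the correlation is near zero, pairing 17 full pairs costs 2 to 3 points of power: 51 to 48%, 81 to 78% and 93 to 91% at 0.7, 1.0 and 1.2 SD. Exact McNemar has a floor: five discordant pairs give at best 2 × 0.5⁵ = 0.0625 and six give 2 × 0.5⁶ = 0.031, so at least six are needed for p < 0.05. With 17 pairs and assumed positivity of 70% versus 30%, its power is 50% at zero within-patient correlation and 64% at 0.3, against 55% and 56% for an unpaired Fisher test. With 8 pairs it is 9% and 6%, which is why sparse binary markers should stay descriptive.
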